APPENDIX A: Schedule of Treatment and Evaluations

	Screening -21 Days	Cycle 1	All Other Cycles	Every 6 Weeks ± 5 Days from Cycle 1-Day 1	End of Study or Early Termination	Follow- up ¹²
Signed Informed Consent	X					
Review Inclusion/Exclusion		X				
Medical History ¹	X					
Physical Examination	X	X	X		X	
Height (cm)	X					
Weight (kg)	X	X	X			
BSA Calculation ²		X	X			
Vital Signs ³	X	X	X		X	
Karnofsky Performance Status	X	X	X		X	
MRI scan / Tumor Assessments	X ⁴			X ⁸	X ^{8,13}	
ECG	X	X ¹⁵	X ¹⁵		X ¹³	
ECHO (with ejection fraction)	X		X ¹¹		X ¹¹	
CBC w/differential & platelets ⁵	X	X ¹⁴	X		X	
Serum Chemistries ^{5,6}	X	X ¹⁴	X		X	
Urinalysis ⁷	X				X	
Serum/Urine Pregnancy Test	X					
ALDOXORUBICIN Administration		X	X			
Concomitant Medications ⁹	X	X	X		X	
Adverse Events ¹⁰		X	X		X	
Telephone Follow-Up						X

NOTE: All assessments must be performed within 72 hours of each specified time parameter, except Cycle 1 (see Section 6 for details).

1. To include concurrent baseline conditions (using NCI CTCAE, version 4.0 [published 28 May 2009] [see Appendix C]), prior cancer therapy (including documentation of prior surgery, adjuvant or neoadjuvant chemotherapy, antibody therapy and radiotherapy).
2. BSA only needs to be calculated if there has been a change >10% in body weight from Cycle 1-Day 1.
3. Blood pressure, pulse, respiratory rate, and temperature. Vital signs will be monitored every 15 minutes starting immediately prior to ALDOXORUBICIN dosing and ending approximately 30 minutes after completion of infusion.
4. MRI scan of brain with contrast to document disease status. If scan was taken within 21 days prior to first dose, a new scan is not necessary. However, if a new scan is to be done, it should be performed within 7 days of starting chemotherapy.
 - a. Historical MRI scans no older than 2 months prior to screening must be electronically submitted to Imaging Endpoints to confirm radiographic progression.
 - b. All scans must be electronically submitted to Imaging Endpoints. Please refer to your Imaging Manual for details.
 - c. If a surgical resection was completed during the screening period and demonstrates disease progression, the MRI may show “non-measurable” disease and will be used to demonstrate disease progression only.

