
Study Population and Main Criteria for Inclusion/Exclusion:
 
Inclusion Criteria: Subjects must meet the following criteria to be included in the study:
 
 1. Age \geq18 years of age; male or female. 2. Histologically or cytologically confirmed unresectable GBM. Subjects with recurrent disease whose prior pathology demonstrated GBM will not need to be re-biopsied. Subjects with prior low-grade glioma or anaplastic glioma are eligible if histological assessment demonstrates transformation into GBM. 3. Cancer progression after treatment with the following: surgery, radiation therapy and temozolomide with no other therapy prior to tumor recurrence. 
 a. Radiographic progression by RANO Working Group Criteria (see Appendix F) will be confirmed by Imaging Endpoints, a central imaging vendor; or b. Confirmation by tumor biopsy if conducted within 4 weeks of Randomization. 4. An interval of at least 12 weeks after last dose of radiation and temozolomide is required, unless cancer progression is proven by diagnostic tumor biopsy. If temozolomide is being used in a maintenance phase, there must be a 28-day washout period prior to Randomization. 5. Stable or decreasing dose of corticosteroids for at least 7 days prior to Randomization. 6. Capable of providing informed consent and complying with trial procedures. 7. Karnofsky Performance Status (see Appendix B) \geq70. 8. Life expectancy \geq8 weeks. 9. Measurable tumor lesions according to RANO Working Group Criteria (see Appendix F). 
 a. In the case that there is "non-measurable" disease due to a radical surgical resection prior to screening, the subject may still qualify if Inclusion #3(b) is met. 10. Women must not be able to become pregnant (e.g. post-menopausal for at least 1 year, surgically sterile, or practicing adequate birth control methods) for the duration of the study. (Adequate contraception includes: oral contraception, implanted contraception, intrauterine device implanted for at least 3 months, or barrier method in conjunction with spermicide.) 11. Women of child bearing potential must have a negative serum or urine pregnancy test at the Screening Visit and be non-lactating. 12. Geographic accessibility to the site, i.e. the ability to come to the study site for each scheduled appointment and evaluation. 
Exclusion Criteria: Subjects meeting the following criteria will not be enrolled:
 
 1. Prior exposure to an anthracycline. 2. Any therapeutic regimen for treatment of recurrent tumor after first line treatment with surgery, radiation and temozolomide. 3. Prior treatment with bevacizumab or an experimental anti-angiogenic agent. 4. Palliative surgery and/or radiation treatment < 4 weeks prior to Randomization. 5. Exposure to any investigational agent within 30 days of Randomization. 6. History of other malignancies (except cured basal cell carcinoma, superficial bladder cancer or carcinoma in situ of the cervix) unless documented free of cancer for \geq3 years. 7. Laboratory values: Screening serum creatinine $>1.5\times$ upper limit of normal (ULN), alanine aminotransferase (ALT) $> 2.5\times$ULN, total bilirubin $>1.5\times$ULN, absolute neutrophil count (ANC) $<1,500/mm^3$, platelet concentration $<100,000/mm^3$, absolute lymphocyte count $<1000/mm^3$, hematocrit level $<27\%$ for females or $<30\%$ for males, serum albumin ≤ 2.5 g/dL, prothrombin time (PT)/ international normalized ratio (INR) $>1.5\times$ULN or $>3\times$ULN on anticoagulant with no evidence of active bleeding. 	

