
Name of Sponsor/Company: CytRx Corporation	
Protocol Number: ALDOXORUBICIN-P2-GBM-01	Phase of Development: 2

8. Anion gap > 16 meq/L or arterial blood pH < 7.30.
 
9. Evidence of central nervous system (CNS) hemorrhage Common Terminology Criteria for Adverse Events (CTCAE) ≥ grade 2 on baseline magnetic resonance imaging (MRI).
 
10. Clinically evident congestive heart failure (CHF) > class II of the New York Heart Association (NYHA) guidelines (see Appendix D).
 
11. Current, serious, clinically significant cardiac arrhythmias, defined as the existence of an absolute arrhythmia or ventricular arrhythmias classified as Lown III, IV or V (Appendix G).
 
12. Baseline QTc >470 msec and/or previous history of QT prolongation.
 
13. History or signs of active coronary artery disease with or without angina pectoris.
 
14. Serious myocardial dysfunction defined as ultrasound-determined absolute left ventricular ejection fraction (LVEF) <45% of predicted institutional normal value.
 
15. Active, clinically significant serious infection requiring treatment with antibiotics, anti-virals, or anti-fungals.
 
16. History of HIV infection.
 
17. Major surgery, except diagnostic tumor biopsy, within 4 weeks prior to Randomization.
 
18. Any condition that might interfere with the subject's participation in the study or in the evaluation of the study results.
 
19. Any condition that is unstable and could jeopardize the subject's participation in the study.
	
Number of Subjects: Up to 28 subjects will be enrolled (14 at each dose level) in 3-5 study centers in the US.	
Test Product, Dose and Mode of Administration: Lyophilized powder in vials that contain 200 mg of ALDOXORUBICIN reconstituted by adding a sterile solution of 50:50 ethanol:water, administration completed within 2 hours (of being reconstituted) as a 30 minute IV infusion in Lactated Ringer's solution. Total doses of either 350 mg/m ² (260 mg/m ² doxorubicin equivalent) or 250 mg/m ² (185 mg/m ² doxorubicin equivalents).	
Reference Therapy, Dose and Mode of Administration: None	
Criteria for Evaluation:	
Efficacy: The following efficacy variables will be evaluated as noted:	

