APPENDIX A: Schedule of Treatment and Evaluations

	Screening -21 Days	Cycle 1	All Other Cycles	Every 6 Weeks ± 5 Days from Cycle 1-Day 1	End of Study or Early Termination	Follow- up ¹²
Signed Informed Consent	X					
Review Inclusion/Exclusion		X				
Medical History ¹	X					
Physical Examination	X	X	X		X	
Height (cm)	X					
Weight (kg)	X	X	X			
BSA Calculation ²		X	X			
Vital Signs ³	X	X	X		X	
Karnofsky Performance Status	X	X	X		X	
MRI scan / Tumor Assessments	X ⁴			X ⁸	X ^{8,13}	
ECG	X	X ¹⁵	X ¹⁵		X ¹³	
ECHO (with ejection fraction)	X		X ¹¹		X ¹¹	
CBC w/differential & platelets ⁵	X	X ¹⁴	X		X	
Serum Chemistries ^{5,6}	X*	X ¹⁴	X		X	
Urinalysis ⁷	X				X	
Serum/Urine Pregnancy Test	X					
ALDOXORUBICIN Administration		X	X			
Concomitant Medications ⁹	X	X	X		X	
Adverse Events ¹⁰		X	X		X	
Telephone Follow-Up						X

NOTE: All assessments must be performed within 72 hours of each specified time parameter, except Cycle 1 (see Section 6 for details).

*Arterial blood gas test, if needed, to confirm acid levels.

CLINICAL PROTOCOL

TITLE: An Open-Label Pilot Phase 2 Study to Investigate the Preliminary Efficacy and Safety of Aldoxorubicin in Subjects with Unresectable Glioblastoma Multiforme Whose Tumors Have Progressed Following Prior Treatment with Surgery, Radiation and Temozolomide

PROTOCOL NUMBER: ALDOXORUBICIN-P2-GBM-01

STUDY DRUG: Aldoxorubicin

IND NUMBER: TBD

SPONSOR: CytRx Corporation
[name]
[name]
[contact]
[contact]

SAFETY [contact]

SAFETY [contact]

DATE OF PROTOCOL: August 9, 2013

CONFIDENTIAL

The information contained in this document is confidential and the proprietary property of CytRx Corporation. Any unauthorized use or disclosure of such information without the prior written authorization of CytRx Corporation is prohibited.

SYNOPSIS

Name of Sponsor/Company: CytRx Corporation	
Protocol Number: ALDOXORUBICIN-P2-GBM-01	Phase of Development: 2
Title of the Protocol: An Open-Label Pilot Phase 2 Study to Investigate the Preliminary Efficacy and Safety of Aldoxorubicin in Subjects with Unresectable Glioblastoma Multiforme Whose Tumors Have Progressed Following Prior Treatment with Surgery, Radiation and Temozolomide	
Primary Objectives: The primary objective of this study is to determine the preliminary efficacy of administration of ALDOXORUBICIN to subjects with unresectable glioblastoma multiforme (GBM) whose tumors have progressed following prior treatment with surgery, radiation and temozolomide.	

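### The entry route for subjects left non-measurable by resection fits the 4-week surgery exclusion only by a narrow path, and the synopsis states no response denominator for them

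*Combined protocol and SAP*

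**What the plan says.** The criteria are in the Amendment 4 synopsis. Inclusion 9 requires measurable lesions by RANO. Its sub-item (a) waives this when the lack of measurable disease is "due to a radical surgical resection prior to screening, the subject may still qualify if Inclusion #3(b) is met". Inclusion 3(b) reads "Confirmation by tumor biopsy if conducted within 4 weeks of Randomization". Exclusion 17 reads "Major surgery, except diagnostic tumor biopsy, within 4 weeks prior to Randomization".

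The schedule table in Appendix A heads its first column "Screening -21 Days". Footnote 4c to the MRI row begins "If a surgical resection was completed during the screening period and demonstrates disease progression"; it goes on to say that the scan may then show non-measurable disease and serves only to show progression. This footnote is printed with Amendment 1. The Amendment 4 table keeps the superscript 4 on the MRI row, but its numbered footnotes are not in the text available.

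Under Statistical Methods (Amendment 4 synopsis), the primary analyses take all randomized subjects with at least one dose and one post-dose efficacy measurement. The percentages with CR or PR, or with SD, are evaluated every 6 weeks. Neither statement mentions measurability at baseline. Objective response is a listed efficacy variable, and the 12-week SD rate is among the other primary objectives. Up to 28 subjects are planned, 14 per dose.

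**The concern.** Inclusion 9(a) is written for someone who has just had a radical resection, and the natural tissue to prove progression in that person is the resection specimen. Footnote 4c describes that use: a resection that itself demonstrates progression. Yet the surgery exclusion exempts a biopsy, not a resection, over the same 4 weeks. A site that reads 9(a) together with 4c could randomize a subject in breach of Exclusion 17. A site that reads Exclusion 17 strictly would turn the same subject away. Footnote 4c also places the resection during screening, whereas 9(a) places it before screening.

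The second issue is analytic. A subject with no measurable lesion at baseline may be unable to register a measurable shrinkage, but the stated analysis set puts that subject in the response denominator. With 14 per arm, a few such subjects can lower the observed rate, or separate the arms if they fall unevenly.

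**Working it through.** **Inputs.** Tissue for 3(b): at most 28 days before Randomization. Exclusion 17: major surgery within 28 days, diagnostic biopsy exempt. Screening: at most 21 days. Arm size: 14, and 2 × 14 = 28 agrees with the stated total. The synopsis gives no alpha, power or effect size, and none is needed here.

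**Step 1: dates.** Let r be the days from resection to Randomization.

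| Case | Inclusion side | Exclusion 17 side | Days that satisfy both |
|---|---|---|---|
| Resection specimen is the 3(b) tissue, day 28 excluded | r ≤ 28 | r > 28 | none |
| Same, day 28 allowed | r ≤ 28 | r ≥ 28 | r = 28 only |
| Resection during screening (footnote 4c) | r ≤ 21 | r > 28 or r ≥ 28 | none |
| Older resection, separate biopsy at b days | b ≤ 28, b < r | r > 28 or r ≥ 28 | r from 29 (or 28) upward |

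The third row does not depend on how the 21 days are anchored. If they run back from the first dose, and Randomization is on or before that day, r is still at most 21.

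**Step 2: response.** Assume k of the 14 subjects in an arm enter through 9(a) and cannot reach CR or PR. With a response rate p in measurable disease, the observed rate is p × (14 − k)/14. The documents give neither p nor k, so a range is shown.

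| k | Highest attainable rate | p = 10% | p = 20% | p = 30% |
|---|---|---|---|---|
| 1 | 92.9% | 9.3% | 18.6% | 27.9% |
| 2 | 85.7% | 8.6% | 17.1% | 25.7% |
| 3 | 78.6% | 7.9% | 15.7% | 23.6% |
| 4 | 71.4% | 7.1% | 14.3% | 21.4% |

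For example, 0.20 × 11/14 = 15.7%.

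**Step 3: stable disease, illustration only.** Take the 8-week PFS in the rationale as an exponential median: 0.5^(12/8) = 35.4% are progression-free at 12 weeks. (That figure is quoted for patients who had failed bevacizumab, whom this trial excludes.) If 20 of those points are responders, the SD rate is 15.4%. Suppose three of 14 enter through 9(a) and count as SD while progression-free. If 35.4%, 50% or 70% of them are progression-free, the rate becomes 19.7%, 22.8% or 27.1%. For the first, (11 × 0.154 + 3 × 0.354)/14 = 19.7%. Per subject that is (19.7 − 15.4)/3 = 1.4 to (27.1 − 15.4)/3 = 3.9 points.

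**The case against.** **The criteria fit together as written.** 3(b) says biopsy and Exclusion 17 exempts a diagnostic biopsy; a conflict appears only if the resection specimen stands in for the biopsy. This is right as far as it goes, and it is why the route is not empty. It leaves a path that needs a second tissue procedure in a subject without measurable tumor, and the text does not say whether the specimen qualifies.

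**Footnote 4c may have lapsed.** Its status under Amendment 4 cannot be confirmed, and it is a note on imaging rather than an eligibility rule. This stands. However, Amendment 1 carries 4c alongside the same wording of 9(a), 3(b) and the surgery exclusion (numbered 16 there), so the mismatch exists within that version. The unanswered question about 3(b) and Exclusion 17 does not need 4c.

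**Little rests on the response rate.** The primary objective is PFS and OS, and the study is a descriptive pilot. At p = 20% and k = 3 the loss is 4.3 points, or 0.6 of a subject, against a standard error of √(0.2 × 0.8/14) = 10.7 points. This limits the importance of the point but does not supply the missing denominator rule.

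**Stronger readings that the documents do not support.** A reader might infer a conflict with Inclusion 2, "Histologically or cytologically confirmed unresectable GBM". The available text does not define that term, and tumor remaining or recurring after a resection might be judged unresectable, so this is at most a tension in wording. A reader might also cite Exclusion 4, "Palliative surgery and/or radiation treatment < 4 weeks prior to Randomization", but a radical resection need not be palliative.

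**Conclusion.** The point holds in a limited form. When the resection specimen is the 3(b) tissue, 9(a) and Exclusion 17 cannot both be met, day 28 exactly aside. A resection during screening, as 4c provides, can never satisfy Exclusion 17 and disagrees with 9(a) on timing. An older resection with a separate biopsy complies.

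The analysis gap is also real in the text available: subjects without measurable baseline disease enter the CR/PR and SD percentages with no distinction. The size of the response effect is that of Step 2 and rests on the assumption that these subjects cannot reach CR or PR. Appendix F would settle that and is not in the text, nor are the fuller protocol sections. The number who enter by this route is unknown.

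A reader might infer that such subjects raise PFS and add 1/14 = 7.1 points each to the SD rate. Neither is shown. Every subject is progression-free when the PFS clock starts, and nothing in the documents says that resected subjects progress later. The 7.1 points is a ceiling; Step 3 gives 1.4 to 3.9 under its own assumptions. An effect on SD or PFS is possible, but its direction and size are unproven. The matter is worth correcting and does not undermine the trial.

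**What to change.** 1. Reconcile Inclusion 9(a), Inclusion 3(b), Exclusion 17 and footnote 4c (if it is still in force), so that they agree on whether a resection specimen satisfies 3(b) and on when the resection may take place. The interval is for the sponsor's clinicians to decide.
2. In the analysis, compute objective response in subjects with measurable disease at baseline, report the number without it by arm, and repeat the 12-week SD rate and PFS without those subjects as a sensitivity analysis.

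The cost is amendment wording and one additional table. The downside is a slightly smaller response denominator, for example 11 instead of 14 if three subjects in an arm enter this way.

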5. During treatment, if any drug-related and/or clinically significant toxicity occurs, retest frequently until stable or resolving and in accordance with GCP. **Note: CBC with differential and platelet count must be performed weekly during each cycle.**
6. To include BUN, phosphorus, magnesium, LDH, creatinine, uric acid, total protein, albumin, calcium, glucose, total bilirubin, ALP, AST, ALT, electrolytes (chloride, sodium, potassium, and bicarbonate), PT/INR (at screening only).
7. Lab urinalysis to include protein, specific gravity, glucose, and blood.
8. Tumor response must be monitored during treatment every 6 weeks \pm 5 days from Cycle 1-Day 1 regardless of dosing delays. The final assessment to be done 3 weeks following final ALDOXORUBICIN administration.
9. To include all medications taken within 30 days prior to study Randomization.
10. Subject will be followed until resolution of any drug-related AE or SAE occurring during the study, including within 30 days of last administration of study medication, or when the subject begins alternative therapy; whichever is sooner.
11. Cycle 4 and End of Treatment visit if later than Cycle 4. Additional testing can be done if clinically indicated.
12. Follow-up by telephone will be conducted in all subjects every 8 weeks to determine date of death.
13. If not done within last 14 days.
14. No need to repeat if performed within 21 days of Randomization.
15. ECGs will be performed pre-dose and at 1 hour post-dose (the anticipated maximal concentration).

CLINICAL PROTOCOL

TITLE: An Open-Label Pilot Phase 2 Study to Investigate the Preliminary Efficacy and Safety of Aldoxorubicin in Subjects with Unresectable Glioblastoma Whose Tumors Have Progressed Following Prior Treatment with Surgery, Radiation and Temozolomide

PROTOCOL NUMBER: ALDOXORUBICIN-P2-GBM-01

STUDY DRUG: Aldoxorubicin

IND NUMBER: 119437

SPONSOR: CytRx Corporation
[name]
[name]
[contact]
[contact]

SAFETY [contact]

SAFETY [contact]

ORIGINAL PROTOCOL: August 9, 2013

AMENDMENT 1: November 12, 2013

AMENDMENT 2: February 4, 2014

CONFIDENTIAL

The information contained in this document is confidential and the proprietary property of CytRx Corporation. Any unauthorized use or disclosure of such information without the prior written authorization of CytRx Corporation is prohibited.

SYNOPSIS

Name of Sponsor/Company: CytRx Corporation	
Protocol Number: ALDOXORUBICIN-P2-GBM-01	Phase of Development: 2

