Primary Objectives: The primary objective of this study is to determine the preliminary efficacy of administration of ALDOXORUBICIN to subjects with unresectable glioblastoma (GBM) whose tumors have progressed following prior treatment with surgery, radiation and temozolomide, as measured by PFS according to the Response Assessment in Neuro-Oncology (RANO) Working Group Criteria (see Appendix F) and OS.	
Secondary Objectives: The secondary objectives of this study are to evaluate the safety of ALDOXORUBICIN in this population assessed by the frequency and severity of adverse events (AEs), abnormal findings on physical examination, laboratory tests, vital signs, echocardiogram (ECHO) evaluations, electrocardiogram (ECG) results, weight, and the change in performance status as measured by the Karnofsky Performance Scale.	
Study Rationale and Significance: ALDOXORUBICIN is a novel prodrug that binds covalently to albumin in the circulation. The drug is accumulated in tumors and doxorubicin is released in the tumor by cleaving the acid labile linker (EMCH) in the low pH tumor environment. This carrier-linked prodrug has demonstrated enhanced anti-tumor activity with reduced toxicity in several murine models when compared with free doxorubicin. Patients with unresectable GBM who have failed prior surgery, radiation and chemotherapy with temozolomide regimens and bevacizumab have an extremely poor prognosis with progression-free survival (PFS) of around 8 weeks and median overall survival (OS) of approximately 8-16 weeks, depending on whether salvage therapy is administered. Recently, we have demonstrated in an orthotopic xenograft model of GBM in mice that ALDOXORUBICIN significantly retards the growth of the tumor and doubles the survival of animals when compared to treatment with either saline or doxorubicin. We have also shown that this molecule collects inside the tumor and not in normal brain parenchyma. Doxorubicin does not penetrate into either the tumor or the brain. Thus, ALDOXORUBICIN may be able to effectively treat patients with advanced GBM that have progressed after standard therapies.	

Name of Sponsor/Company: CytRx Corporation	
Protocol Number: ALDOXORUBICIN-P2-GBM-01	Phase of Development: 2

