
Study Design and Methodology: This is a phase 2 open-label, pilot study evaluating the preliminary efficacy and safety of ALDOXORUBICIN administered at either 350 mg/m² (260 mg/m² doxorubicin equivalent) or 250 mg/m² (185 mg/m² doxorubicin equivalent) intravenously on Day 1, every 21 days until evidence of tumor progression, unacceptable toxicity or withdrawal of consent. Subjects will be randomly assigned to either dose of ALDOXORUBICIN. G-CSF (Neupogen or Neulasta) should be administered as primary prophylaxis to all subjects according to the ASCO Guidelines (see Appendix E). Note: ALDOXORUBICIN, at higher doses, has been associated with >20% incidence of grade 3 or 4 neutropenia. Therefore, the administration of G-CSF should occur even during Cycle 1 for subjects receiving the 350 mg/m² dose of ALDOXORUBICIN.
 
Tumor response (complete response [CR], partial response [PR] and stable disease [SD]) will be monitored at Screening, then every 6 weeks (±5 days) using the RANO Working Group Criteria (see Appendix F), and treatment will continue every 21 days until tumor progression is observed, unacceptable toxicity occurs, or consent is withdrawn. Median PFS, PFS at 12 and 18 weeks, and 6 months, SD rate at 12 weeks, and OS will be monitored as other primary objectives. Subjects will visit the study site every 21 days for their IV infusions, at which time safety monitoring, including AEs, a directed physical examination, laboratory evaluations (serum chemistry and complete blood count [CBC]), vital signs, weight measurements, Karnofsky Performance Status (see Appendix B), documentation of corticosteroid usage and ECGs will be performed. All subjects will have blood drawn for serum electrolytes to evaluate the anion gap prior to each drug administration. Cardiac function will also be followed periodically using ECHOs.
	

Name of Sponsor/Company: CytRx Corporation	
Protocol Number: ALDOXORUBICIN-P2-GBM-01	Phase of Development: 2

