
 • PFS • OS • Objective tumor response (RANO Working Group Criteria [see Appendix F]) • PFS at 12 and 18 weeks and 6 months • SD rate at 12 weeks • Pseudo progression events on DSC-MRI in subjects who undergo additional MRI sequence evaluation • Karnofsky Performance Status (see Appendix B) • Corticosteroid usage 	

Name of Sponsor/Company: CytRx Corporation	
Protocol Number: ALDOXORUBICIN-P2-GBM-01	Phase of Development: 2

Safety: The following safety variables will be assessed over the course of the study:
 
 • AEs • Ability to remain on assigned treatment (tolerability) • Clinical and laboratory data including physical examinations, vital signs, weight, ECHO evaluations, ECG results and laboratory test results • Use of concomitant medications 	

Statistical Methods: In accordance with the intention-to-treat principle, all randomized subjects who enter active treatment and have had at least 1 dose of study medication and 1 post-dose efficacy measurement will be included in the primary statistical analyses.
 
Efficacy: Tumor response by MRI will be monitored every 6 weeks (± 5 days) until disease progression. For the estimation of PFS and OS a Kaplan-Meier analysis will be performed. The percentage of subjects with CRs or PRs, or SD will be evaluated every 6 weeks.
 
Safety: The safety data will be summarized for all subjects. Total number of AEs leading to withdrawal and abnormal laboratory tests will be evaluated. AEs, ability to remain on assigned treatment (tolerability), and abnormal findings on physical examinations, vital signs, weight, ECG results, ECHO, laboratory test results, and use of concomitant medications, will be assessed to characterize the safety profile of the treatment regimen. Descriptive evaluation denoting the changes from baseline to the final assessment visit with respect to key laboratory parameters and vital signs will also be provided.
	

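### The primary efficacy set is labelled intention-to-treat but requires a dose and an undefined post-dose measurement, so early deaths can be dropped and Kaplan-Meier PFS and OS biased upward

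*Combined protocol and SAP*

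**What the plan says.** In the Amendment 4 synopsis, Statistical Methods, the sentence that defines the primary analysis set opens "In accordance with the intention-to-treat principle, all randomized subjects who enter active treatment" and continues "have had at least 1 dose of study medication and 1 post-dose efficacy measurement will be included in the primary statistical analyses". The same sentence stands in the August 2013 protocol and in every amendment.

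The primary measures are PFS by RANO and OS, both estimated by Kaplan-Meier. The efficacy variables under Criteria for Evaluation include PFS, OS, tumour response, Karnofsky status and corticosteroid usage. Nothing says which of these supplies the required measurement, or whether a death does.

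On timing:
- MRI is due every 6 weeks (±5 days) from Cycle 1 Day 1.
- Footnote 8 of Appendix A, printed with Amendment 1, adds "The final assessment to be done 3 weeks following final ALDOXORUBICIN administration".
- Karnofsky status and corticosteroid usage are recorded at the dosing visits: "Subjects will visit the study site every 21 days for their IV infusions".

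Two other rules cover everyone. The Safety paragraph of Statistical Methods says "The safety data will be summarized for all subjects", and footnote 12 of Appendix A (Amendment 1) says "Follow-up by telephone will be conducted in all subjects every 8 weeks to determine date of death".

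**The concern.** Both conditions for entering the primary set arise after randomisation, so it is an efficacy-evaluable set and not an intention-to-treat set. The dose condition alone breaks the label.

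The measurement condition matters more for the estimates. Requiring a later measurement before a subject enters a survival curve amounts to requiring survival to that measurement. A subject who dies first is removed from both the events and the number at risk, and every later survival estimate rises.

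The trial has no reference therapy, so the absolute PFS and OS at each dose are its main output. With 14 subjects per dose, one or two missing deaths visibly move an estimate. A report that carried only the intention-to-treat label would not show this. The same deaths would still appear in the safety summary, so the two parts of the report would rest on different subjects without saying so.

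**Working it through.** **Plan's own figure.** The only design number is up to 28 subjects, 14 per dose: 14 × 2 = 28. The supplied text gives no power or precision basis, and this point needs none.

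**Step 1: who is lost under each reading of the measurement.**

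| Reading | First opportunity | Dosed subject who dies earlier |
|---|---|---|
| MRI | Week 6, or about 3 weeks after the last dose if stopped early | Dropped |
| Karnofsky or corticosteroid record | 21-day visit (week 3) | Dropped |
| Death counts as an OS measurement | Date of death | Kept |

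Subjects who progress or stop early and attend the termination visit stay in. Subjects lost alive without assessment add little or no PFS bias and can shift OS either way. Undosed subjects are out on every reading, with no known direction of bias.

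**Step 2: effect per dropped death (no survival model needed).** Without censoring, dropping k early deaths from N multiplies every later Kaplan-Meier value by N/(N − k). For N = 14 the factor is 14/13 = 1.077 for k = 1 and 14/12 = 1.167 for k = 2. An illustrative milestone of 5/14 = 35.7% becomes 5/13 = 38.5% or 5/12 = 41.7%. The same factor applies to OS and, if death is a PFS event as is usual, to PFS.

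**Step 3: how many deaths could be lost.** Inputs: t = 6 or 3 weeks from the schedule, and M = median OS of 30 to 40 weeks, which is an assumption because the documents give no figure for this population.

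- Exponential: p = 1 − 2^(−t/M).
- If a fraction f of early deaths is dropped, the shift in the median is −M·log2(1 − f·p). With f = 1 this equals t.
- Weibull, shape 1.5 (risk rising over time): p = 1 − exp(−ln 2·(t/M)^1.5). With all early deaths dropped, the shift is M·[(1 + (t/M)^1.5)^(2/3) − 1].

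Ranges below run over M = 30 to 40.

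| Scenario | Week 6: share lost | Week 6: shift in median OS | Week 3: share lost | Week 3: shift in median OS |
|---|---|---|---|---|
| Exponential, all dropped (upper bound) | 9.9–12.9% (1.4–1.8 of 14) | 6 weeks | 5.1–6.7% (0.7–0.9 of 14) | 3 weeks |
| Exponential, half dropped | 4.9–6.5% | 2.9 weeks | 2.5–3.4% | 1.5 weeks |
| Weibull 1.5, all dropped | 4.0–6.0% | 1.5–1.8 weeks | 1.4–2.2% | 0.55–0.63 weeks |
| Death counts as a measurement | 0 | 0 | 0 | 0 |

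**Step 4: why the documents' OS figure is not used as the expected rate.** The rationale gives a median OS of 8 to 16 weeks. The exponential formula would then give 22.9–40.5% lost at week 6 and 12.2–22.9% at week 3. That prognosis is for patients who failed "chemotherapy with temozolomide regimens and bevacizumab have an extremely poor prognosis". Here "Prior treatment with bevacizumab or an experimental anti-angiogenic agent" is an exclusion, and entry requires Karnofsky of at least 70 and life expectancy of at least 8 weeks. Early loss should be lower.

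**The case against.** The strongest reply is that the bias depends on a reading and on text we do not have. The supplied material is synopses and schedules. The schedule refers to a Section 6, so a fuller body exists and may define the measurement or keep early deaths in. OS and PFS head the list of efficacy variables, so a recorded death might itself qualify. This stands as a limit on certainty: the loss of early deaths is possible, not established. It does not rescue the label, because undosed subjects are excluded either way.

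The second reply is about size. Only the exponential, week-6, every-death-dropped case gives more than one expected loss per dose. Under the Weibull case, the chance that a dose loses nobody is 42–57% at week 6 and 74–82% at week 3. The exact 95% interval for 5/14 is 12.8% to 64.9%, so one dropped death (2.7 points) is small beside sampling error. That is true, and it lowers the expected effect. But the error from dropped deaths runs in one direction, and the confidence interval does not reflect it.

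Third, the sentence does state its conditions openly, and an all-treated set could be defended in an open-label pilot with no between-dose test in the supplied text. Both points are fair. An all-treated set would meet the main concern if it were named as such and kept early deaths in.

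Last, the wording of footnotes 8 and 12 comes from Amendment 1. The Amendment 4 schedule keeps the markers, but the supplied text does not repeat the notes, so unchanged wording is assumed.

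**Conclusion.** The concern holds and should be fixed. It is certain that the set is not intention-to-treat. On the MRI or visit-record reading, subjects who die before the measurement are dropped and later PFS and OS estimates rise. On the reading that death counts, no dosed death is lost.

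The documents do not determine the size. The firm part is the factor of 1.077 or 1.167 per dose for one or two dropped deaths, given 14 subjects and no censoring. The shift in median OS, from about 0.6 weeks up to a bound of 6 weeks, rests on the assumed 30 to 40 week median, the shape of the hazard and the share of early deaths dropped. The supplied text contains no separate OS population and no rule that keeps early deaths in, though such a rule could sit in a section not supplied.

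**What to change.** In Statistical Methods:

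- Make the primary PFS and OS analysis all randomised subjects by assigned dose. At minimum use all dosed subjects, named as such.
- State that death without a post-baseline scan is a PFS event on the date of death.
- Because the wider set brings in unassessed subjects, give rules for them: censor PFS at day 1 if alive with no assessment, and count them as non-responders and as not disease-controlled.
- Define the post-dose efficacy measurement, and keep the present set as a sensitivity analysis labelled evaluable. Report the number excluded from it per dose, with reasons.

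The cost is one or two sentences. No new data are needed, since telephone follow-up for date of death already covers all subjects. The downside for the sponsor is that reported PFS and OS may be slightly less favourable.
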